3.3. Benefit/Risk Assessment

Based on information about relamorelin obtained to date, the benefits of study participation are expected to include accelerated GE and clinically meaningful improvement in the symptoms of DG, including nausea, abdominal pain, postprandial fullness, bloating, vomiting frequency, early satiety, and vomiting severity. A potential risk of treatment is worsening of glycemic control, including the possibility of diabetic ketoacidosis occurring. However, preventive measures, including special laboratory assessments to allow early recognition by investigators and participants of rising glucose levels, are being included in this protocol so that early remedial action (eg, adjustment of medication and diet) may be taken to minimize increase in glucose levels; this might increase the incidence of hypoglycemic reactions, especially in participants with T1DM. See Section 5 Study Design for details of study procedures, dose, and study design justification.

More detailed information about the known and expected benefits and risks and reasonably expected AEs associated with relamorelin are provided in the investigator's brochure (Relamorelin Investigator's Brochure); information about the investigational directions for use (DFU) for the pen injector, the device that will be used to administer study treatment are also provided.

Relamorelin

4. Objectives and Endpoints

Objectives	Endpoints

Primary
 
 • To compare the efficacy of relamorelin with placebo in participants with DG with respect to a composite of the following core signs and symptoms of DG: 
 • Nausea • Abdominal pain • Postprandial fullness • Bloating • To compare the efficacy of relamorelin with placebo in participants with DG with respect to vomiting frequency 	
Primary
 
 • Change from Baseline to Week 12 in the weekly DGSSS. Baseline is defined as the average of the 2 weekly DGSSS from the 2-week placebo Run-in Period. • Vomiting Responder, defined as a participant with zero weekly vomiting episodes during each of the last 6 weeks of the 12-week Treatment Period

Secondary
 
 • To compare the efficacy of relamorelin with placebo in participants with DG with respect to the following individual symptoms of the DGSSS: 
 • Nausea • Abdominal Pain • Postprandial fullness • Bloating • To compare the safety of relamorelin with placebo in participants with DG 	
Secondary
 
 • Individual Symptom (ie, nausea, abdominal pain, postprandial fullness, and bloating) Responder, defined as a participant with at least a 2-point decrease in the change from baseline on the weekly average of the symptom severity (at its worst) during each of the last 6 weeks of the 12-week Treatment Period • AEs, clinical laboratory values, vital signs, ECGs, HbA1c, and anti-relamorelin antibodies

4.1. Clinical Hypotheses

The clinical hypotheses are:

- 1) DG participants receiving relamorelin compared with DG participants receiving placebo will experience greater improvement in DGSSS.
- 2) A greater proportion of DG participants receiving relamorelin than DG participants receiving placebo will achieve “Vomiting Responder” status, defined as a participant with zero weekly vomiting episodes during each of the last 6 weeks of the 12-week Treatment Period.

██████████
Relamorelin

5. Study Design

[figure not shown]
5.1. Overall Design

- Global, multicenter, randomized, double-blind, placebo-controlled, parallel-group
- Treatment Groups: Relamorelin 10 µg or placebo, twice daily, SC
- Study Duration: Up to 18 weeks, including a 12-week Treatment Period
- Study Periods: A Screening Period of up to 4 weeks, a 2-week Run-in Period, and a 12-week Treatment Period as follows:
 - Run-in Period: Participants who meet initial study entry criteria during the Screening Period will enter a 2-week placebo Run-in Period, during which they will self-administer single-blind placebo twice daily, SC. Using an electronic hand-held device, participants will report their symptoms via the Diabetic Gastroparesis Symptom Severity Diary (DGSSD) as well as their ██████████ compliance, and use of rescue medication.
 - 12-week Treatment Period: Participants who meet entry criteria at the end of the Run-in Period, will be randomized 1:1 to blinded treatment with relamorelin 10 µg or placebo. Participants will continue to use the electronic hand-held device for reporting of their symptoms via the DGSSD as well as their ██████████ compliance, and use of rescue medication.

See [Figure 2](#) for Study Schematic

Relamorelin

Figure 2: RLM-MD-02 Study Schematic

Relamorelin

Study Population:

- Screening: Males and females aged 18 years and older; T1DM or T2DM with controlled and stable blood glucose levels and HbA1c \leq 11%; symptoms suggestive of DG for at least 3 months, with mechanical obstruction of the gastrointestinal (GI) tract as the cause of symptoms having been ruled out; history of at least 2 vomiting episodes.
- During the Run-in Period: At least 1 vomiting episode and delayed GE by gastric emptying breath test (GEBT)
- After Run-in Period: Evidence of compliance during the Run-in Period with the use of the electronic hand-held device for entry of data, with twice daily SC injections of the study treatment, no treatment with GI promotility agents during the Run-in Period, at least 1 vomiting episode reported during the 2-week Run-in Period; and a score of \geq 16 for the average of the daily DGSSS assessments measured during the Run-in Period.

For studies conducted at US (IND) sites and non-US (non-IND) sites, data from IND and non-IND study sites will be pooled together for analysis.

Assuming they meet entry criteria, participants who successfully complete this study are eligible to enter a placebo-controlled, long-term safety and efficacy study (RLM-MD-03) during which they will receive study treatment for an additional 46 weeks.

5.2. Participant and Study Completion

Approximately 2500 participants will be screened at approximately 350 study sites (globally) to achieve 600 participants randomly assigned to study treatment (300 participants per treatment group). A total of 480 participants are expected to complete the study (240 participants per treatment group). See Section 10.1 for details on sample size determination.

5.3. End of Study Definition

The end of the study is defined as the date of the last visit of the last participant in the study.

A participant is considered to have completed the study if he/she has completed all phases of the study including at least 84 days of treatment, and the last visit (Visit 7). Independent of the end of study definition, all laboratory tests with values considered clinically significantly abnormal during participation in the study or within 30 days after the last dose of study treatment should be repeated until the values return to normal or baseline or are no longer considered clinically significant by the investigator or MSP.

Relamorelin

5.4. Scientific Rationale for Study Design

The sponsor has designed this randomized, double-blind, placebo-controlled, parallel-group study to follow regulatory recommendations for conduct of Phase 3 therapeutic confirmatory studies, specifically the ICH Harmonized Tripartite Guideline E8 (General Considerations for Clinical Trials, Current Step 4 version dated 20 July 2000) and Guideline E10 (Choice of Control Group and Related Issues in Clinical Trials, Current Step 4 version dated 17 July 1997). The study also has been designed to comply with recommendations made by the US FDA, Center for Drug Evaluation and Research (CDER) in the Draft Guidance for Industry, [Gastroparesis: Clinical Evaluation of Drugs for Treatment, July 2015](#), including those for the minimum duration of studies to show efficacy (at least 12 weeks) and inclusion as part of the development plan of a long-term placebo-controlled safety study (12 months, with appropriate pre-specified provisions for rescue medications).

Several design features have been incorporated in the current study in an effort to minimize bias, including a placebo run-in and double-blind design. Random assignment of participants avoids bias and helps ensure that both known and unknown risk factors are distributed evenly between treatment groups. The use of a placebo control permits prospective comparison between the relamorelin group and the control group. Furthermore, the placebo run-in period with collection of data (symptoms in a daily diary) was incorporated into this study to allow study personnel to assess compliance with and tolerability of these procedures prior to randomization, and to obtain robust baseline measurements prior to initiating study treatment dosing. The run-in period also allows the confirmation of vomiting symptoms in addition to a history of vomiting.

5.5. Justification for Dose

[figure not shown]
Study RM-131-009 was a 12-week Phase 2b, randomized, double-blind, placebo-controlled, parallel group study to evaluate the safety and efficacy of relamorelin in diabetic participants with moderate to severe DG. The doses included within the study were 10 µg BID, 30 µg BID, and 100 µg BID. In general, all doses tested within RM-131-009 appeared to demonstrate meaningful reductions in overall DG symptom scores including vomiting episodes, with acceptable safety and tolerability. The frequency of vomiting episodes was reduced from baseline over the 12-week Treatment Period to a similar extent for participants who received the 3 doses of relamorelin and placebo. Based upon the observed dose response of change-from-baseline symptom scores collected daily over the course of 12 weeks using the DGSSD, the 30 µg BID, and 100 µg BID doses demonstrated apparent maximal symptom score improvements, while the 10 µg BID dose achieved near maximal improvements. Of note, the twice-a-day regimen of relamorelin appears to be necessary for effective symptom relief; the 10 µg once daily study treatment did not demonstrate significant improvement in symptom relief compared to placebo after 28 days of dosing in Study RM-131-004.

Review of the safety laboratory data collected in RM-131-009 revealed an apparent dose-related increase in HbA1c values. Although the variability in HbA1c response was high across all treatments, the 30 µg BID and 100 µg BID doses demonstrated apparent maximal changes in HbA1c values, while the 10 µg BID dose resulted in an approximately half-maximal increase

██████████
Relamorelin

10. Able to provide written informed consent (IC) prior to any study procedures and willing and able to comply with study procedures (as defined in Appendix 3)

6.2. Exclusion Criteria

Participants are excluded from the study if any of the following criteria apply:

[figure not shown]
3. Participants who are actively experiencing anorexia nervosa, binge-eating, bulimia, or other eating disorder at the time of Screening (Visit 1) are excluded regardless of when diagnosis was established.

Relamorelin

[figure not shown]
4. History of intestinal malabsorption (including celiac disease even if well-controlled on a gluten-free diet) or pancreatic exocrine insufficiency; also, history of non-celiac gluten sensitivity
5. History of belching disorders, other nausea and vomiting disorders (eg, chronic nausea and vomiting syndrome, cyclic vomiting syndrome, cannabinoid hyperemesis syndrome), or rumination syndrome

10. Currently receiving parenteral feeding or presence of a nasogastric or other enteral tube for feeding or decompression

██████████
Relamorelin

24. Functional dyspepsia diagnosed before the diagnosis of diabetes mellitus

Relamorelin

their advanced symptoms and, therefore, are unlikely to benefit from further pharmacological intervention have been excluded. Although GP invariably affects negatively the ability of participants to achieve optimum diabetic control, an attempt to achieve stable and controlled blood glucose levels must be made by the patient prior to enrollment.

6.3. Lifestyle Restrictions

There are no specific dietary restrictions in the study. It is expected that participants are aware of the importance of maintaining reasonable consistency in timing and size of meals (and specifically carbohydrate intake) for achieving adequate control of hyperglycemia but appreciate that the presence of GP may make this difficult.

For timing of meals around the GEBT, refer to the Study Reference Manual.

6.4. Screen Failures

Screen failures are defined as participants who consent to participate in the clinical study but are not subsequently randomly assigned to study treatment. Screen failures can fail to meet criteria for random assignment to study treatment in the study either before or after participation in the Run-in Period.

Participants who do not meet the criteria for participation in this study (screen failure) before entering the Run-in Period may be rescreened once if the reason for screen failure is only because of Inclusion Criterion 3 “HbA1c \leq 11.0% at Screening (Visit 1).” In this specific situation, the patient may be rescreened after at least one month and no more than 6 months of further effort to achieve improved glycemic control, as indicated by HbA1c being \leq 11.0%.

Rescreening of a participant for any other reason is up to the discretion of the Sponsor and must be approved by the Sponsor prior to any rescreening procedures. The timeframe for rescreening is up to 6 months from the time of screen failure. Participants who enter the Run-in Period will not be allowed to be rescreened. Rescreening requires that a participant be assigned a new participant number and after repeating the Informed Consent Process, undergo all original screening assessments.

The sponsor may permit a participant with a positive UDS by immunoassay, at Screening (Visit 1) to continue in the Screening Period while confirmatory urine drug screen testing by a more specific method is carried out on an aliquot of the original urine sample. If the confirmatory test is negative, the initial positive urine drug screen will be considered to have been a false-positive urine drug screen and the participant can continue in screening. Confirmatory testing will be done at the discretion of the sponsor and must be approved by the sponsor prior to analysis. The significance of a positive UDS result for drugs prescribed for the participant (ie, barbiturates, benzodiazepines, amphetamines, but not opioids or cannabinoids) should be assessed by the investigator as to whether their stable-dose usage is clinically appropriate, and if so, should not be exclusionary; use of these prescribed drugs on an as-needed basis is not allowed.

Relamorelin

Table 7-1: Study Treatment Details

Study Treatment	Relamorelin	Placebo
Dosage Formulation	Pre-Filled Cartridge in Multi-dose Pen Injector	Pre-Filled Cartridge in Multi-dose Pen Injector
Unit Dose Strength	10 µg dose	N/A
Route of Administration	Subcutaneous	Subcutaneous
Dosing Instructions	Administer twice daily	Administer twice daily
Packaging and Labeling		
Manufacturer	Allergan (Assembled Pen)	Allergan (Assembled Pen)
Injection Device	Utilize Multi-dose Pen Injector for the administration of the study treatment or placebo.	Utilize Multi-dose Pen Injector for the administration of the study treatment or placebo.

7.1.1. Run-in Medications and Administration

Placebo (single-blind) should be self-administered twice daily

SC using the pen-injector.

7.1.2. Study Supplies

1. The Allergan-manufactured medical devices provided for use in this study are: (1) Prefilled Cartridge, and (2) Multi-dose Pen Injector.
2. Instructions for medical device use are provided in Relamorelin Pen Investigational Directions for Use.
3. Medical device incidents, including those resulting from malfunctions of the device, must be detected, documented, and reported by the investigator throughout the study (see [Appendix 7](#)).

Relamorelin

7.2. Dose Modification

Not applicable.

7.3. Method of Treatment Assignment

All participants will be centrally assigned to randomized study treatment using an interactive web response system (IWRS). Before the study is initiated, the log-in information and directions for the IWRS will be provided to each site.

At the beginning of the 12-week Treatment Period, eligible participants will be randomized in a 1:1 ratio to blinded treatment with relamorelin 10 µg or placebo. Randomization will be stratified by geographic region.

Study treatment will be dispensed at the study visits indicated in the Schedule of Activities (SoA) (Section 2).

Returned study treatment should not be re-dispensed to the participants.

7.4. Blinding

The investigator, investigational staff, and participant will be fully blinded to study treatment during the 12-week Treatment Period; during the placebo Run-in Period, single-blind treatment with placebo is self-administered. All study treatment will be provided in identical pen injectors and cartons to maintain blinding of the study.

7.5. Preparation/Handling/Storage/Accountability

1. The investigator or designee must confirm appropriate temperature conditions have been maintained during transit for all study treatment received and any discrepancies are reported and resolved before use of the study treatment.
2. Only participants enrolled in the study may receive study treatment, and only authorized site staff may supply or administer study treatment. All study treatments must be stored in a secure, environmentally controlled, and monitored (manual or automated) area in accordance

Relamorelin

with the labelled storage conditions with access limited to the investigator and authorized site staff.

3. The investigator, institution, or the head of the medical institution (where applicable) is responsible for study treatment accountability, reconciliation, and record maintenance (ie, receipt, reconciliation, and final disposition records).
4. Further guidance and information for the final disposition of unused study treatment are provided in the Study Reference Manual.

7.6. Treatment Compliance

Study treatment compliance will be closely monitored by assessing the participant's daily reporting of self-administered study treatment on the electronic hand-held device. Before dispensing new study treatment, study site personnel will make every effort to collect all unused study treatment. In the event of AE or intercurrent illness, dosing of study treatment can be stopped temporarily, for a maximum duration of 3 days. Should longer cessation of dosing be necessary, the investigator should contact the sponsor (Section 8.1.1).

The study centers will keep an accurate drug disposition record that specifies the amount of study treatment dispensed to each participant and the date of dispensing.

7.7. Concomitant Therapy

Any medication or vaccine (including over-the-counter or prescription medicines, vitamins, and/or herbal supplements) that the participant is receiving at the time of enrollment or receives during the study must be recorded on the electronic case report form (eCRF) along with:

- Reason for use
- Dates of administration including start and end dates
- Dosage information including dose and frequency

As much as possible, the dose and frequency of all concomitant medications taken for chronic conditions with the exception of diabetes mellitus (see Section 7.7.2) should be held stable during the study. The sponsor should be contacted if there are any questions regarding concomitant or prior therapy.

7.7.1. Prohibited Treatments

[figure not shown]
The classes of drugs prohibited in the study are, with the exception of SGLT-1 and SGLT-2 inhibitors, those that affect GI motility, either positively or negatively, and therefore could confound the assessment of the efficacy of study treatment on the signs and symptoms of DG. The SGLT-1 and SGLT-2 inhibitors are-prohibited for 3 days prior to the GEPT done at the start of the Run-in Period in all participants and in a subset of participants at a subset of sites at Visit 7

Relamorelin

or the Early Termination Visit. Their mechanism of action is through causing increased glycosuria, which may affect interpretation of the GEBT results.

Table 7-2 provides a list of drug classes and treatments that are prohibited during the study and require washout during the placebo Run-in Period.

Table 7-2: Prohibited Medications and Washout Requirements

Relamorelin

7.7.2. Permitted Treatments

Any medication or vaccine (including over-the-counter or prescription medicines, vitamins, and/or herbal supplements) that the participant is receiving at the time of enrollment or receives during the study must be recorded in the eCRF along with:

- Indication
- Dates of administration including start and end dates
- Dosage information including dose and frequency

DG participants enrolled in this study will likely consist mostly of participants receiving one or more prescription medications for blood-glucose control. Good clinical practice allows for frequent adjustment of medication by participants and their health care providers to minimize large fluctuations in glycemia, and this practice is encouraged in this study. It should be remembered that certain diabetic drugs (see [Table 7-2](#)) delay GE and are prohibited during this study. Other therapy considered necessary for the participant's welfare may be given at the discretion of the investigator. If the permissibility of a specific medication/treatment is in question, please contact the sponsor.

The sponsor or designee should be contacted if there are any questions regarding concomitant or prior therapy.

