Prior medication is defined as any medication started before the date of the first dose of double-blind study treatment. *Concomitant medication* is defined as any medication taken on or after the date of the first dose of double-blind study treatment. Any prior medications started more than 30 days before the date of the first dose of double-blind study treatment and any concomitant medications started after the date of the last dose of double-blind study treatment will not be presented in the summary tables, but will be included in the participant data listings.

Both prior and concomitant medication use will be summarized by the number and proportion of participants in each treatment group for the Safety Population. The *WHO Drug Dictionary*, Version B2 March 2017 or newer, will be used to classify prior and concomitant medications by WHO Drug Anatomical/Therapeutic/Chemical category and drug preferred name. Multiple medications used by a participant will only be counted once for the coded drug preferred name or therapeutic class.

9.0

Extent of Exposure and Treatment Compliance

9.1

Extent of Exposure

Exposure to the study treatment for the Safety Population during the double-blind treatment period will be summarized for treatment duration, calculated from the eDiary as the number of days from the date of the first dose of study treatment to the date of the last dose of study treatment, inclusive. Descriptive statistics (number of participants, mean, SD, median, Q1, Q3, minimum, and maximum) will be presented by treatment group. The date of first dose is the date of randomization(date of baseline visit).

Patient-years, defined as duration of exposure to the study treatment in years, will be summarized by treatment for the Safety Population.

9.2

Measurement of Treatment Compliance

Dosing compliance for a specified period is defined as the number of injections actually taken by a participant during that period divided by the number of injections expected for the same period multiplied by 100. The number of injections actually taken is obtained from the participants' responses in the item of 'How many injections of study medication have you administered today?' from the electronic hand-held device. The number of injections expected during a period is the number of days in the period multiplied by 2.

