Potassium	mmol/L	< 0.9 * LLN	> 2.0 * ULN
Glucose, Fasting	mmol/L	< 0.9 * LLN	> 2.5 * ULN
Glycohemoglobin A1C	%		Increase of ≥ 0.5%
Glycohemoglobin A1C	%		Increase of ≥ 1%
Sodium	mmol/L	< 0.9 * LLN	> 1.1 * ULN
Total Bilirubin	µmol/L	—	> 1.5 * ULN
Total Protein	g/L	< 0.9 * LLN	> 1.1 * ULN
Triglycerides, Fasting	mmol/L	—	≥ 3 * ULN
Urea (BUN)	mmol/L	—	> 1.2 * ULN
Magnesium	mmol/L	< 0.9 * LLN	> 1.1 * ULN
Bicarbonate	mmol/L	< 0.9 * LLN	> 1.1 * ULN
Phosphate	mmol/L	< 0.9 * LLN	> 1.1 * ULN
Uric Acid	µmol/L	< 0.9 * LLN	> 1.1 * ULN
HEMATOLOGY			
Basophils Absolute Cell Count	10 ⁹ /L	—	> 3 * ULN
Eosinophils Absolute Cell Count	10 ⁹ /L	—	> 3 * ULN
Hematocrit	Ratio	< 0.9 * LLN	> 1.1 * ULN
Hemoglobin	g/L	< 0.9 * LLN	> 1.1 * ULN
Lymphocytes Absolute Cell Count	10 ⁹ /L	< 0.8 * LLN	> 1.5 * ULN
MCH	PG	—	> 3 * ULN
MCHC	G/L	—	> 3 * ULN
MCV	fL	< 0.9 * LLN	> 1.1 * ULN
Monocytes Absolute Cell Count	10 ⁹ /L	—	> 3 * ULN
Neutrophils Absolute Cell Count	10 ⁹ /L	< 0.8 * LLN	> 1.5 * ULN
Platelet Count	10 ⁹ /L	< 0.5 * LLN	> 1.5 * ULN

Table 11.2-1. Criteria for Potentially Clinically Significant Laboratory Tests

Parameter	SI Unit	Lower Limit	Higher Limit
Red Blood Cell Count (Erythrocyte Count)	$10^{12}/L$	< 0.9 * LLN	> 1.1 * ULN
White Blood Cell Count	$10^9/L$	< 0.7 * LLN	> 1.5 * ULN
URINALYSIS			
pH		< 0.9 * LLN	> 1.1 * ULN
Specific Gravity		—	> 1.1 * ULN

LLN: Lower limit of normal value provided by the laboratory.

ULN: Upper limit of normal value provided by the laboratory.

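### HbA1c is summarised by arm with no account of antidiabetic intensification, so the tables cannot be read as relamorelin's own glycaemic effect

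*Protocol*

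**What the plan says.** **The risk.** Protocol 3.3 states: "A potential risk of treatment is worsening of glycemic control". Protocol 3.2 reports rising HbA1c after relamorelin was started in Phase 2b. Protocol 5.5 calls the rise dose-related and says that "the 10 µg BID dose resulted in an approximately half-maximal increase"; that is the dose under study here. Section 4 of the protocol lists the safety endpoints as "AEs, clinical laboratory values, vital signs, ECGs, HbA1c, and anti-relamorelin antibodies".

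**The response to the risk.** Protocol 7.7 asks for stable chronic medication, but diabetes is exempt: "with the exception of diabetes mellitus (see Section 7.7.2) should be held stable during the study". Protocol 7.7.2 allows frequent changes "to minimize large fluctuations in glycemia, and this practice is encouraged in this study". Protocol 3.3 gives the direction: "early remedial action (eg, adjustment of medication and diet) may be taken to minimize increase in glucose levels". Protocol 9.4.6 makes self-monitored glucose, HbA1c and fasting glucose available to investigators for these decisions.

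**The analysis.** SAP 11.5 places HbA1c with the other laboratory tests. SAP 11.2 gives descriptive change from baseline by arm and counts potentially clinically significant values. The lower HbA1c criterion in Table 11.2-1 is "Increase of ≥ 0.5"%, and the other is a rise of at least 1%. A participant is counted if at least one post-baseline value meets the criterion, and SAP 16.4 uses every post-baseline assessment for this purpose.

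**The medication tables.** SAP 8.0 says: "Both prior and concomitant medication use will be summarized by the number and proportion of participants in each treatment group". Each participant counts once per drug name or class. A drug is concomitant if taken on or after the first double-blind dose, whenever it was started.

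**The concern.** The plan expects relamorelin may raise glucose, and the protocol offers a remedy that lowers it again. With blinded investigators applying the same judgement in both arms, a drug that raises glucose would lead to more intensification in its own arm. The HbA1c tables then show the drug's effect net of the response to it.

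What is at stake is interpretation. A small HbA1c difference could mean that the drug has little effect on glycaemia, or that control was held by added agents or higher doses. The two carry different messages for the benefit-risk assessment, and no visible summary table tells them apart.

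**Working it through.** **1. Figure to reproduce.** None. The plan states no effect size, SD or power for HbA1c, so the check compares the planned outputs and then illustrates the mechanism.

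**2. Which planned output would show intensification?**

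| Output | New agent | Dose increase | HbA1c rise |
|---|---|---|---|
| Mean HbA1c change (SAP 11.2, 11.5) | no | no | net of treatment |
| Counts of rises of at least 0.5% and 1% (SAP 11.2, 16.4) | no | no | kept if present at any draw; missed if prevented before every draw |
| Medication tables (SAP 8.0) | mixed with continued drugs | no | not applicable |
| Fasting glucose (SAP 11.2) | no | no | same netting applies |
| Hyper- and hypoglycaemia events (SAP 11.1.1) | no | no | only events judged clinically significant (Protocol 9.2.7.2) |

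New starts cannot be recovered by comparing the prior and concomitant tables either. SAP 8.0 leaves prior drugs begun more than 30 days before first dose out of the summary tables, so the prior table is not a baseline list of antidiabetic therapy.

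**3. Direction.** Let D be the difference in mean HbA1c change without intensification, p_R and p_P the shares intensified on relamorelin and placebo, and L the mean lowering per intensified participant, taken as equal in both arms. Then

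observed difference = D − (p_R − p_P) × L.

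It is smaller than D whenever p_R exceeds p_P.

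**4. Illustration.** Every input here is an assumption: D = 0.30 or 0.50 point, L = 0.5 to 1.0 point.

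*Chosen gap in intensification.* With p_R − p_P = 0.10 to 0.30, the amount removed runs from 0.10 × 0.5 = 0.05 to 0.30 × 1.0 = 0.30. The observed difference is then 0.25 down to 0.00 for D = 0.30, and 0.45 down to 0.20 for D = 0.50.

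*Same rule in both arms.* Suppose 70% of participants whose HbA1c would rise by at least a trigger T are intensified. Take normal changes with SD 0.8 to 1.2, a placebo mean of zero, and T = 0.5 or 1.0. Then p_P = 0.7 × P(Z ≥ T/SD) and p_R = 0.7 × P(Z ≥ (T − D)/SD). For SD 1.0, T = 0.5 and D = 0.50:
- p_P = 0.7 × 0.309 = 0.216
- p_R = 0.7 × 0.500 = 0.350
- gap = 0.134
- observed difference = 0.50 − 0.134 × 1.0 = 0.37, or 0.50 − 0.134 × 0.5 = 0.43

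Over the whole grid, D = 0.30 appears as 0.21 to 0.27, and D = 0.50 as 0.34 to 0.45.

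**5. Limit of the illustration.** It concerns the mean at a single draw. It does not carry over to the threshold counts, because a rise seen at an earlier draw remains an event after it is treated. How many rises are prevented before every draw depends on the HbA1c schedule, which is not visible in the available text. I give no figure for the counts.

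**The case against.** - **The threshold rule is more robust than it looks.** A reader might infer that a rise which is treated away counts as no event. SAP 11.2 and 16.4 do not support that: any post-baseline value meeting the criterion counts. This stands, and it confines the problem to mean change and to rises prevented before every draw.
- **HbA1c is not the main safety comparison.** A reader might also infer that the trial would declare glycaemic safety from this table. The documents list HbA1c as one of several safety items and summarise it descriptively, with no test, margin or decision rule. This stands.
- **Comparing randomised arms under adjusted care is legitimate.** It is a valid description of HbA1c in practice. That is correct; what it does not give is the drug's own glycaemic effect.
- **Other tables help.** Fasting glucose and the hyper- and hypoglycaemia events give partial cover, and newly started agents do add to the medication counts. The cover is partial for the reasons in the table above.
- **Adjustment can go down as well as up.** True of Protocol 7.7.2, and Protocol 3.3 anticipates more hypoglycaemia. Protocol 3.3 nevertheless describes the remedial step as limiting increases in glucose. The direction of the bias remains conditional on more intensification on relamorelin.
- **A composite triggered by any insulin up-titration would be noisy.** It could dilute the contrast between arms. This stands and shapes the fix.
- **The criticised tables may not be produced.** SAP 4.0 says that the trial was terminated and only an abbreviated report will follow. The appendix defining it is not visible, so a relevant analysis there cannot be excluded.

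**Conclusion.** The point holds as a cheap improvement. The visible plan does not report antidiabetic intensification by arm, although the protocol encourages adjustment and expects it in response to the very risk that HbA1c is meant to monitor. The planned tables are sound as a description of HbA1c under adjusted care, but not as an estimate of relamorelin's own effect on glycaemia.

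If intensification is more frequent on relamorelin, mean change is attenuated toward no difference, and so are the counts to the extent that rises are prevented before every draw. The documents do not allow the size to be computed. The same-rule illustration removes roughly a tenth to a third of the mean difference (0.027/0.30 = 9% to 0.164/0.50 = 33%), wholly on assumed inputs. A reader might go further and infer that most of the signal is hidden. That requires stacking the upper assumptions, and nothing in the documents supports them.

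The SAP already accepts the principle for efficacy: Section 10.6 tabulates rescue use by arm and repeats the primary analyses with affected weeks set to missing.

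**What to change.** In SAP 11.2 and 11.5, for the Safety Population, tabulate by arm the participants with:

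- (a) a new antidiabetic agent started after the first double-blind dose;
- (b) a recorded dose increase of an existing agent, shown separately from (a).

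Use the start date, dose and frequency that Protocol 7.7 and 7.7.2 already require in the eCRF. State how partial start dates are handled, since SAP 16.9.1 can set them to the first-dose date.

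Beside the HbA1c-only counts, show a supportive composite: a rise of at least 0.5% (and, separately, at least 1%) or a new antidiabetic agent. Add dose increases only in a second version, under a size or persistence rule fixed before unblinding. Add a note that the HbA1c-only tables describe control under adjusted care.

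**Cost.** One derived intensification variable with its two components, and one descriptive table. No new data are collected and no treatment decision changes. Insulin dose records may be incomplete and routine titration adds noise, which is why (a) and (b) stay apart. Given the termination, apply this to whichever HbA1c tables the abbreviated report still contains.
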